## 14.5 Methods of Analysis

### 14.5.1 Primary Endpoint

The primary efficacy analysis will be performed in the full analysis set (FAS). For the analysis of the primary endpoint fall (yes, no) within 6 months a time-to-event methodology will be applied using the time to the first fall to account for potentially incomplete observation times of the patients. This is considered to be more efficient than an analysis of the binary endpoint fall (yes, no), and therefore leading to a gain in power. The time to first fall will be calculated from date of handing out the study book to the first fall. For patients who do not fall within the 6 months observation period, the time to last contact will be used as censored observation. Death without previous fall will be regarded as competing event in the analysis. A Cox regression model will be used to test the efficacy of EYT versus Tai Chi versus standard care in reducing the risk of falling within 6 months after handing out the study book. The model will include intervention type, study site, BBS score, and age as independent variables. To account for multiplicity issues in this three-group comparison, a closed test procedure at two-sided level alpha of 5% will be used, i.e. the global null hypothesis of no differences between any of the three intervention types will be tested first, and if it can be rejected, pairwise group comparisons will be conducted each at two-sided level alpha of 5%. Hazard ratios (HR) between interventions will be calculated from the model with two-sided 95% CI. Cumulative incidences for both competing events will be graphically displayed. In addition to the overall comparison of the treatment arms, a comparison of treatments in key patient subgroups is of interest. The treatment effect will be estimated separately in patients defined by different diagnoses (present vs. absent) from regression models including the interaction between treatment and diagnosis. The diagnoses investigated include: cardiovascular, orthostatic dysregulation, pulmonal, diabetes, other internistic, osteoporosis, mental condition, sleep disorder, history of stroke, Parkinson disease, multiple sclerosis, polyneuropathy, other neurological, chronic arthritis of knee or hip or feet, other musculoskeletal.

Depending on the patients included in the trial, some of the diagnoses might not be analyzed, since there might be no patient with that diagnosis.

As a sensitivity analysis these analyses above will be repeated in the PP.

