### **5.3 Randomisation – general and methodological considerations**

After baseline assessment (see sections 5.2 and 6.3) batches of ideally 15 patients should be randomised to the 3 research arms: EYT or Tai Chi or standard care alone (control). In exceptional cases – e.g. when recruitment is much slower or faster than expected - 12 or 18 patients can be randomised at once, respectively.

If possible, two batches of 15 (or 12 or 18) patients should be enrolled and randomised to 2 x 3 groups. If two batches with 15 (12, 18) patients are randomised concurrently (or within a few days), it is recommended to subdivide the batches depending on their risk of falling (BBS), to randomise one batch of 15 (12, 18) patients with lower BBS and one batch of 15 (12, 18) patients with higher BBS.

The randomisation code will be generated by the CTU using the following procedure to ensure that treatment assignment is unbiased and concealed from patients and investigator staff. For each batch size (12, 15 and 18) a separate randomisation fax form and randomisation lists will be prepared. Randomisation will be stratified by clinical site and performed in blocks of length 12, 15 or 18 in a ratio of 1:1:1. The randomization code will be produced by validated programs based on the Statistical Analysis System (SAS).

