by the study sites. It also enables the patient for self-help. Neither therapists nor teacher nor study personal is meant to comment, recommend or dissuade on any standard care measures or any other fall prevention measures.

*How:* EYT and Tai Chi will be provided in one-hour group sessions, á 5 ( $\pm$  1) patients. These group sessions start with an appreciating discussion about practicing (see section 9), followed by practicing the exercises and – if appropriate – ending with a resting time (approximately 15 minutes). Patients are instructed to practice at home at a minimum of 20 minutes on 3 non-class days.

*Where:* EYT and Tai Chi will be provided in appropriate rooms: They should be easily accessible with public transportation, if possible, located nearby the patients (e.g. in retirement homes, meeting places of senior citizens, churches, at the study sites, in doctor's facilities or in rooms provided by EYT therapists or Tai Chi teachers). The room should be accessible for those with disabilities, should support the patients to feel comfortable, to exercise freely (size 50-70 m^2, minimum 36 m^2), friendly bright, quiet, without distraction, properly ventilated and heatable, with no cold stone floor. One chair per patient (stable and safe) has to be provided. Restrooms should be easy accessible, on the same floor.

*When:* EYT and Tai Chi will be provided first twice/week (week 1-12) and then once/week (week 13-24). The intensity is higher in the first 12 weeks (twice per week), taking into account the learning curve, and reduced to once per week during the second 12 weeks when individually practicing has become more routine. Participants are instructed to practice exercises at home.

*Tailoring:* Tai Chi and EYT exercises follow the manuals but are individually tailored to the capabilities of the participants. When exercises beyond the manual are used, this will be documented by the EYT therapists or Tai Chi teacher, together with the reason for using them. In case of significant deterioration of health condition or a new diagnosis during month 1-6, affecting safety of the patient and participation in group classes, the EYT therapist or Tai Chi teacher should contact the investigator whether group sessions should be interrupted.

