### 14.3 Sample Size Calculation

Sample size calculation is based on assumptions on the proportion of patients with at least one fall during a 6-months period. The proportion of patients with at least one fall is assumed as 50% in the standard care group [50, 59]. A decrease of this proportion to 35% is considered as clinically relevant and as achievable by EYT as well as by Tai Chi [63]. The study is planned with 80% power to show a difference between treatments at two-sided level alpha of 5%, when proportions of fallers are 50% with standard care and 35% both with EYT and with Tai Chi. Based on the chi-square distribution, this requires 155 patients per group (calculated with NQuery Advisor 7.0). The sample size calculation was performed for the three-group comparison. To account for multiplicity issues in this three-group comparison, a closed test procedure at two-sided level alpha of 5% will be used, i.e. the global null hypothesis of no differences between any of the three intervention types will be tested first, and if it can be rejected, pairwise group comparisons will be conducted each at two-sided level alpha of 5%. The two-group comparison of EYT versus standard care has a power of 80%, when the proportion of fallers is reduced from 50% to 34.3%. The two-group comparison of EYT versus Tai Chi has a power of 80%, when the difference in the proportion of fallers is 15%. To account for a certain amount of non-compliance and incomplete observations, 550 patients will be randomised in a ratio of 1:1:1.

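### EYT and Tai Chi are taught in small classes, but the stated Cox and negative binomial models have no term or variance for class, so their intervals are somewhat too narrow

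*Protocol*

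**What the plan says.** **Delivery.** Section 8.1 states that "EYT and Tai Chi will be provided in one-hour group sessions", with 5 (± 1) patients per group, twice weekly in weeks 1 to 12 and once weekly in weeks 13 to 24. A therapist (EYT) or teacher (Tai Chi) leads each session. Section 5.3 says "batches of ideally 15 patients should be randomised to the 3 research arms", with 12 or 18 in exceptional cases, so a batch yields one class of five (four or six) in each active arm. Standard-care patients receive a brochure and advice and have no group sessions.

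**Analysis.** For the primary Cox model, section 14.5.1 states "The model will include intervention type, study site, BBS score, and age as independent variables". Section 14.5.2 repeats that list for the negative binomial model of the number of falls. Hazard ratios and incidence rate ratios with 95% intervals are calculated from these models. The global test of three arms opens a closed procedure in which every test is at two-sided 5%.

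**Sample size.** Section 14.3 assumes power of 80% "when proportions of fallers are 50% with standard care and 35% both with EYT and with Tai Chi", and adds: "Based on the chi-square distribution, this requires 155 patients per group". It also says: "The sample size calculation was performed for the three-group comparison". The increase to 550 is attributed to non-compliance and incomplete observation.

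Nowhere does the protocol mention a class or leader effect, a random effect, a robust variance or an ICC.

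**The concern.** Classmates share a leader, a room and each other's company for 24 weeks. The protocol itself counts social support among the active ingredients (section 1.1), and section 9 makes the group atmosphere depend on its leader. Outcomes within a class may therefore be more alike than outcomes of two patients from different classes of the same arm. Classes are nested within arm and site, so a main effect of site cannot absorb this variation.

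If the model variance treats patients as independent, standard errors are too small. That affects the global test and every pairwise test. The closed procedure gives no protection, because it controls the familywise error only if each component test holds its own level. EYT versus Tai Chi is affected most, since both sides are clustered. Active versus standard care is affected least, since one side is not.

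**Working it through.** **Step 1: does the planned sample size contain a clustering allowance?** Inputs from section 14.3: 50% / 35% / 35%, two-sided alpha 5%, power 80%, 155 per arm. For the three-group chi-square test (2 df) with independent patients, λ = n Σ(pᵢ − p̄)² / [p̄(1 − p̄)].

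- p̄ = 0.40 and Σ(pᵢ − p̄)² = 0.01 + 0.0025 + 0.0025 = 0.015
- λ = n × 0.015 / 0.24 = 0.0625 n, which is 9.69 at n = 155
- Power is 80.2% at n = 155 and 79.96% at n = 154

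The stated 155 is reproduced exactly under independence, so it contains no design effect.

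**Step 2: error of tests that ignore class.** Assumptions: class size m = 5 (section 8.1), equal arms, and an ICC of 0.01 to 0.10, which is assumed because the protocol gives none. The variance of an active arm's estimate is multiplied by DE = 1 + (m − 1) × ICC = 1 + 4 × ICC; standard care keeps 1.

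- Correct SE / naive SE, active versus standard care: √[(1 + DE)/2]
- Correct SE / naive SE, EYT versus Tai Chi: √DE
- True pairwise error: 2[1 − Φ(1.96 / ratio)]
- Global test under the null: the naive statistic behaves as DE·χ²₁ + [(2 + DE)/3]·χ²₁ (independent terms), but is compared with 5.99

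| ICC | DE | SE ratio, active vs standard care | Error | SE ratio, EYT vs Tai Chi | Error | Global error |
|---|---|---|---|---|---|---|
| 0 | 1.00 | 1.000 | 5.0% | 1.000 | 5.0% | 5.0% |
| 0.01 | 1.04 | 1.010 | 5.2% | 1.020 | 5.5% | 5.4% |
| 0.05 | 1.20 | 1.049 | 6.2% | 1.095 | 7.4% | 7.1% |
| 0.10 | 1.40 | 1.095 | 7.4% | 1.183 | 9.8% | 9.4% |

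Worked row, ICC 0.05: √[(1 + 1.20)/2] = 1.049 and 1.96/1.049 = 1.87, giving 6.2%; √1.20 = 1.095 and 1.96/1.095 = 1.79, giving 7.4%.

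**Step 3: check in a Cox model.** A null simulation used 37 batches of 15, a frailty shared within active classes of five, no covariates and 4,000 runs per setting. The ICC is that of the binary fall outcome.

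| ICC (approx.) | Global | Active vs standard care | EYT vs Tai Chi |
|---|---|---|---|
| 0 | 4.9% | 4.7% | 5.5% |
| 0.02 | 6.8% | 5.7% | 6.3% |
| 0.04 | 7.3% | 6.5% | 7.4% |
| 0.10 | 8.8% | 7.3% | 9.7% |

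Monte Carlo error is about 0.3 to 0.5 points, so the simulation agrees broadly with step 2.

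**Step 4: power when clustering is respected.** This uses a 2-df Wald test at 50% / 35% / 35% with the active-arm variances multiplied by DE. Without clustering it gives 79.8% at 155 per arm and 86% at 183 per arm. At ICC 0.01 / 0.05 / 0.10, power is 79% / 77% / 75% at 155 per arm and 86% / 84% / 82% at 183 per arm.

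**The case against.** **The SAP may settle the variance.** Section 14.5.1 lists covariates; it neither prescribes nor excludes a robust variance, and section 14 leaves detail to an SAP that is not at hand. A cluster-robust variance would leave the listed model and its hazard ratio unchanged. This is a fair point, and independence is inferred from silence. But the protocol does fix the model terms and says that the intervals come from the model, and the default reading is model-based variance. Section 14 would require a departure to be marked and justified.

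**The effect is modest.** This stands. Classes of five limit the design effect, and at an ICC of 0.01 the excess error is under half a percentage point. Reducing falls against standard care is the main question, and that comparison is the least affected.

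**Stronger readings that the protocol does not support.**

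- A reader might infer that omitting the randomisation batch, or shared calendar time, makes matters worse. Allocation is balanced within batch, and standard-care patients start at a comparable time (section 5.2). A batch effect is therefore shared by all three arms, and ignoring it is conservative. BBS, on which concurrent batches may be split, is already in the model.
- A reader might count tailoring as a shared class effect. Sections 8.1 and 14 do not say so: section 8.1 describes tailoring to the capabilities of individual participants.
- A reader might infer that all secondary analyses are affected. Beyond the number of falls, section 14.5.2 says only that appropriate regression models will be used, so nothing is fixed wrongly there.
- A reader might expect a far larger error from leaders who teach several classes. With one leader per site and method and a log-hazard SD of 0.2 between leaders, a simulation gave a global error of 14%. That is only an illustration: the protocol does not state the number of leaders, and section 6.2 provides for their replacement.

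**Conclusion.** The point holds, at modest size. As stated, the Cox and negative binomial analyses ignore class membership in two of three arms. For any positive within-class correlation their intervals are too narrow and their nominal 5% tests anti-conservative.

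For an assumed ICC of 0.01 to 0.10 and classes of five, the correct SE exceeds the naive SE by about 2 to 18% for EYT versus Tai Chi and 1 to 10% for active versus standard care. The corresponding error rates are those in the step 2 table. The direction does not depend on the assumed ICC; the size does.

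A reader might also infer that the trial is underpowered. The figures do not show that: at 183 per arm, power stays at or above 80% up to an ICC of 0.10, provided that none of the reserve is lost. With 155 evaluable per arm it falls to about 75% at that ICC. The defect is mainly in the variance estimate.

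**What to change.** In sections 14.5.1 and 14.5.2, keep the listed covariates and state that the Cox and negative binomial models use cluster-robust variance with a small-sample correction. The cluster is the randomised exercise class in the EYT and Tai Chi arms; each standard-care patient is a singleton. Base the global test, the pairwise tests and the intervals on this variance. The small-sample correction matters: in simulation at an ICC of about 0.03 and 0.08, uncorrected class-level robust SEs still left 6 to 7% error. Robust variance is preferable to a shared frailty for the primary analysis because it leaves the meaning of the hazard ratio unchanged, whereas a frailty makes it conditional on class.

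Add a sensitivity analysis with therapist or teacher as the cluster, because one leader may teach several classes.

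Decide this before the blind review. Classes exist only in the active arms, so their correlation cannot be examined without looking at allocation.

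The cost is mainly wording. The class follows from batch and arm, and attendance is documented by the leaders (section 6.4); the leader of each class must be available in the data. Intervals widen slightly. The power loss from ICC 0 to 0.05 is about 2 to 3 points (79.8% to 77% at 155 per arm; 86% to 84% at 183).

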Risk factors for falls include [19]: age, female gender, past history of a fall, lower-extremity weakness, cognitive impairment, loss of sensory system functions (e.g. proprioceptive sensitivity, vestibular system, vision, hearing), Parkinson disease, osteoarthritis of the knee, diabetes, cerebrovascular or cardiovascular disease, history of stroke, orthostatic hypotension, balance problems, dizziness, anaemia, drugs affecting the central nervous system, number of medications of any type, recent changes in the dose of medication, type of footwear and safety hazards in the home environment.

Disability-adjusted life year (DALY) rates caused by falls are 5,000-7,000 per 100,000 men and women aged 80 and older [20]. After femoral neck fractures only 33-40% of patients regain their prior basic everyday competences (eating, body care) and 14-21% their competence for instrumental activities (like shopping, phone calls). After falls and hip fracture, 30-50% of people express fear of falling reducing physical activity, mobility, self-confidence and increasing falls, social isolation, institutionalization, and mortality [3, 21].

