#### 4.1 Inclusion Criteria

- Adults 65 years or older.
- Chronic disease (musculoskeletal, neurologic, internistic)
- Increased risk of falling (Berg Balance Scale (BBS) score 49 or less).
- Self-reported history of imbalance (*Anamnestisch: Unsicherheit beim Gehen oder Stehen*)
- Living in the community (at own home) or retirement or nursing home.
- Ability to participate in 1-hour group-based sessions (medical assessment).
- Able to leave home on their own at least twice per week (e.g. for doctors visit, shopping)
- Patient's written informed consent has been obtained

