### **6.3 Baseline Assessment:**

Sociodemographic data, history, diagnoses, risk factors including:

- Age, gender, highest completed level of education and training, height, weight, BMI.
- Falls within last 6 months, with/without injuries), use of walking aid.
- Trouble vision, trouble hearing, vertigo, trouble walking.
- Diagnosis, (cardiovascular, orthostatic dysregulation, pulmonal, diabetes, other internistic, osteoporosis, mental condition, sleep disorder, history of stroke,

Parkinson disease, multiple sclerosis, polyneuropathy, other neurological, chronic arthritis of knee or hip or feet, other musculoskeletal).

- Sport/physical activity
- Social activity (living alone, with family, friends; socializing/meeting with friends, relatives, neighbours; social support through family, friends, neighbours.

The document asking for diagnoses should be signed by the investigator to make sure that patients understood and filled it out correctly

BBS is assessed by a study personnel, as well as MoCA and IADL, supported by written instructions.

The questionnaires *Short Falls Efficacy Scale-International*, *GDS-15*, *SF-12*, *ICPH*, *FIMA* are filled in by the patients. Study personnel will support patients to fill in questionnaires, particularly the *FIMA*, and check them for completeness. Also family members/next of kin or health care professionals can support patients to fill in the questionnaires (see do's and don'ts at table).

The questionnaires should be completed in the same environment, quiet and respectful of the subject's privacy and prior to other investigations. Patient reported questionnaires are to be filled out by the patient him/herself. It is important that the investigator or other study personnel do not influence the patient in any way during the completion of the questionnaire (see do's and don'ts at table).

The following checklist contains some “do's” and “don'ts” when administering the questionnaires (except baseline questions).

DOs	DON'Ts
Do have the subject complete the questionnaire and make sure questionnaire are filled in completely	Do not discuss the subject's health, health data, or emotions with them before they fill out the questionnaire
Do be warm, friendly and helpful	Do not force or command subjects to fill out the questionnaire

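### Both fall models leave out baseline fall history, a collected and named risk factor, so a probably modest gain in power is not taken

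*Protocol*

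**What the plan says.** Section 14.5.1 fixes the covariates of the primary Cox model: "The model will include intervention type, study site, BBS score, and age as independent variables". Section 14.5.2 repeats the list for the negative binomial model of number of falls and extends the analyses to 12 months.

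Section 1.1 includes past falls in its list of risk factors: "age, female gender, past history of a fall, lower-extremity weakness, cognitive impairment". Section 6.3 collects at baseline: "Falls within last 6 months, with/without injuries), use of walking aid". That look-back has the same length as the primary observation period. Entry under section 4.1 requires "Self-reported history of imbalance", not a previous fall, so fall history can differ between patients.

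Randomisation is stratified by site only, with a recommended split of concurrent batches by BBS (section 5.3). The planned subgroup models in section 14.5.1 use diagnoses. Fall history therefore enters neither the design nor the fall analyses, and no reason is given.

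**The concern.** The covariate list is a choice the protocol makes, not a detail it leaves open. When a variable that predicts the outcome is left out of a Cox model, the estimated treatment hazard ratio lies closer to 1 than the covariate-conditional one. In a negative binomial model the omitted variable adds to the unexplained dispersion. Either way some power is given up, although the data are already due to be collected.

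The omission also sits awkwardly with the protocol's own reasoning. Section 14.5.1 prefers time-to-event analysis to a binary analysis because it gains power, and section 14.6 adjusts health-care costs for their baseline value. What is at stake is precision for the primary comparison and for the fall count.

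**Working it through.** **1. The plan's own figure.** Inputs from section 14.3: fallers 50%, 35% and 35%, two-sided 5%, 80% power, with the result "Based on the chi-square distribution, this requires 155 patients per group".

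For a three-group chi-square test (2 df) the noncentrality is λ = n·Σ(p − p̄)² / [p̄(1 − p̄)].

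- p̄ = (0.50 + 0.35 + 0.35)/3 = 0.40
- Σ(p − p̄)² = 0.0100 + 0.0025 + 0.0025 = 0.015
- λ = 155 × 0.015 / 0.24 = 9.69, giving power 80.2% (154 per group gives 79.96%)

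The 155 reproduces. So does the pairwise statement: 50% versus 34.3% at 155 per group gives 80.2%. Both are unadjusted calculations that take no credit for any covariate.

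**2. Time to first fall, with and without fall history.** The protocol gives no strength for fall history, so the following are assumptions:

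- Fall history is binary, with prevalence 30% or 50% and hazard ratio 1.5, 2 or 3.
- BBS is a standardised score with hazard ratio 1.5 per SD, and has latent correlation 0.4 with fall history.
- Times to first fall are exponential, with hazard λ₀·exp(ln HR_T·active + ln 1.5·BBS + ln HR_H·history), where the BBS term is signed so that worse balance raises the hazard.
- λ₀ and HR_T are solved so that 6-month fallers are 50% under standard care and 35% in each active arm.

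Both fitted models contain BBS; only one contains fall history. Site and age were not simulated. The closed test was followed: a global 2-df Wald test, then the pairwise test at 5%. There were 2,000 trials per row. Power for EYT versus standard care (%), without → with fall history:

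| History HR | Prevalence | 155 per arm | Gain | 183 per arm | Gain |
|---|---|---|---|---|---|
| 1.5 | 50% | 79.3 → 80.0 | 0.7 | 86.0 → 86.5 | 0.5 |
| 1.5 | 30% | 78.4 → 79.4 | 1.0 | 85.2 → 85.8 | 0.6 |
| 2.0 | 50% | 80.2 → 81.8 | 1.6 | 86.8 → 88.2 | 1.4 |
| 2.0 | 30% | 80.4 → 83.4 | 3.0 | 86.0 → 87.6 | 1.6 |
| 3.0 | 50% | 82.3 → 86.0 | 3.7 | 87.6 → 92.2 | 4.6 |
| 3.0 | 30% | 81.8 → 88.4 | 6.6 | 86.8 → 92.0 | 5.2 |

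The 183 per arm is 550/3, the number actually to be randomised. The simulation error of a single power figure is about √(0.80 × 0.20/2000) = 0.9 points. The two models were fitted to the same simulated data, so the differences are more precise than that.

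**3. Number of falls.** Assumptions: mean 1 fall per 6 months, dispersion 1, rate ratio 0.70 for treatment, 183 per arm, 800 trials per scenario, BBS not in the model. Global power without → with fall history:

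- history rate ratio 2: 61.8% → 65.8%, a gain of 4.0 points
- history rate ratio 3: 55.6% → 61.9%, a gain of about 6 points
- history rate ratio 1 (no effect): 67.4% → 67.4%

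**4. Room in the Cox model.** At 155 per arm the planned proportions give 155 × (0.50 + 0.35 + 0.35) = 186 first falls. With 8 sites the model has 2 + 7 + 1 + 1 = 11 parameters. Two more make 13, or 186/13 ≈ 14 events per parameter.

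**The case against.** The list is prespecified and defensible. It holds the stratification factor, age, and BBS, which section 4 presents as a predictor of falls with a stated risk gradient. Section 1.1 names many risk factors without ranking them, and being listed and collected does not oblige anyone to adjust. All of this stands, and it is why the point concerns efficiency rather than error.

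Four stronger readings are tempting, and the documents do not support them.

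- *The trial is underpowered because of the omission.* Section 14.3 claims "The study is planned with 80% power to show a difference between treatments at two-sided level alpha of 5"% for an unadjusted test, and that figure reproduces.
- *The treatment effect is biased, or imbalance in prior fallers goes uncorrected.* Randomisation protects the comparison, and chance imbalance is already covered by the test's error rate. The pull toward 1 is the difference between a conditional and a less conditional hazard ratio.
- *The gain is larger.* If fall history is taken as independent of BBS and BBS is left out of the model, pairwise power at 155 per arm goes from 73.4% to 76.5% at hazard ratio 2 and from 73.8% to 80.7% at 3. BBS is in the planned model and is meant to predict falls, so independence is doubtful. The trial also randomises about 183 per arm.
- *The baseline item is the outcome measured earlier.* The outcome comes from a prospective daily diary with monthly ascertainment and explicit exclusions (sections 2.2 and 6.4). The baseline item is a recalled history, and nothing says that those exclusions apply to it or that a count is recorded.

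Section 14 also lets the SAP make marked and reasoned changes. That makes the point easy to settle, but it does not change what the protocol now fixes.

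**Conclusion.** The point holds as a minor to moderate efficiency improvement. Both fall models omit a variable that the protocol itself names as a risk factor and collects, and no reason is given.

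For EYT versus standard care through the closed test, the gain at 155 per arm is about 1 point at hazard ratio 1.5, 2 to 3 at 2, and 4 to 7 at 3. At about 183 per arm it is roughly 0.5, 1.5 and 5 points. For fall counts, global power rises by about 4 to 6 points at rate ratios 2 to 3, a figure that would probably be smaller with BBS in that model.

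All of these rest on assumed prognostic strength, prevalence and correlation with BBS. If fall history adds little beyond BBS and age, the gain is near zero. The direction is firm; the size is not.

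**What to change.** Add falls in the 6 months before baseline as a covariate to the primary Cox model, the negative binomial model and the 12-month repeats of both. State the coding and let it follow the baseline form: yes/no, or 0, 1, and 2 or more if a count is captured. State also how a missing answer is handled, so that no randomised patient drops out of the full analysis set. Fix all of this before any outcome data by arm are seen, and mark it in the SAP as a change from the protocol with its reason, as section 14 requires.

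The cost is one sentence of text and one or two model parameters. No new data are needed, and the sample size calculation does not change.
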